**5.2 Use of co-intervention**

Not applicable.

**5.3 Escape medication (if applicable)**

Not applicable.

**6. INVESTIGATIONAL PRODUCT**

Not applicable, as this study does not involve an investigational product.

**6.1 Name and description of investigational product(s)**

Not applicable, as this study does not involve an investigational product.

**6.2 Summary of findings from non-clinical studies**

Not applicable, as this study does not involve an investigational product.

**6.3 Summary of findings from clinical studies**

Not applicable, as this study does not involve an investigational product.

**6.4 Summary of known and potential risks and benefits**

Not applicable, as this study does not involve an investigational product.

**6.5 Description and justification of route of administration and dosage**

Not applicable, as this study does not involve a medicinal product.

**6.6 Dosages, dosage modifications and method of administration**

Not applicable, as this study does not involve a medicinal product.

**6.7 Preparation and labelling of Investigational Medicinal Product**

Not applicable, as this study does not involve a medicinal product.

**6.8 Drug accountability**

Not applicable, as this study does not involve a medicinal product.

## **7. NON-INVESTIGATIONAL PRODUCT**

### **7.1 Name and description of non-investigational product(s)**

Patients will undergo percutaneous transhepatic biliary drainage with SEMS placement. Name and description are summarized in the Product Characteristics, see appendix A.

### **7.2 Summary of findings from non-clinical studies**

These are summarized in the Product Characteristics, see appendix A.

### **7.3 Summary of findings from clinical studies**

These are summarized in the Product Characteristics, see appendix A.

### **7.4 Summary of known and potential risks and benefits**

These are summarized in the Product Characteristics, see appendix A.

### **7.5 Description and justification of route of administration and dosage**

Not applicable, as this study does not involve a medicinal product.

### **7.6 Dosages, dosage modifications and method of administration**

Not applicable, as this study does not involve a medicinal product.

### **7.7 Preparation and labelling of Non Investigational Medicinal Product**

Not applicable, as this study does not involve a medicinal product.

### **7.8 Drug accountability**

Not applicable, as this study does not involve a medicinal product.

## 8. METHODS

### 8.1 Study parameters/endpoints

#### 8.1.1 Main study parameter/endpoint

- OS, defined as the interval between the day of intervention and date of death or last follow-up. This will be estimated using the Kaplan-Meier method;

#### 8.1.2 Secondary study parameters/endpoints

- Stent-related complications according to Clavien-Dindo grading system within 90 days (see Table 2.).
- Absolute and relative (%) bilirubin decrease after 14 days.
- Number of scheduled and unscheduled reinterventions within 90 days.
- Infectious biliary complications (i.e. cholangitis and cholecystitis);
- Technical success of stent placement at initial drainage procedure;
- Bile culture results;
- QoL, measured with the EORTC Quality of Life Questionnaire C-30 (QLQ-C30) and its biliary cancer module (QLQ-BIL21) (see Appendix C and D);
- Proportion of patients that became eligible for palliative chemotherapy, based on bilirubin level below 20 mmol/l and good performance status (ECOG < 2);
- Cost-effectiveness.

#### 8.1.3 Other study parameters (if applicable)

Not applicable.

### 8.2 Randomisation, blinding and treatment allocation

Not applicable.

### 8.3 Study procedures

#### Before stent placement

- Full eligibility check as described in section 4.
- Written informed consent

#### Laboratory tests

##### **During stent placement**

- Bile cultures and next-generation sequencing of bile cell-free DNA.
- When histological confirmation is lacking:

- Percutaneous liver- or peritoneal biopsies are performed (only if liver- or distant metastases are present).
- Or
- Intraductal biopsies and brush cytology are performed as follows:
    - Samples from the stricture are taken using a cytology brush by moving the brush five times back and forth through the stricture.
    - Brush is performed two times and both brushes are placed in Cytolyt medium. Cytology and Next Generation Sequencing will be performed (on indication) at the Pathology Department (according to Erasmus MC, UMC Utrecht, Amsterdam UMC and Oslo University Hospital protocol).
    - Three or four intraductal forceps biopsies are performed.
    - Histological confirmation can be obtained through frozen section procedure before the SEMS is placed.

#### **After stent placement (i.e. follow-up)**

- Serum bilirubin is measured at T1(14 and 28 days). One blood sample of 10 ml will be taken.

#### **Follow up**

Follow-up appointments are planned as deemed necessary by the treating specialist, but at least 14 days (T1), one month (T2) and three months (T3) after stent placement. Each follow-up will take 30 minutes. During T1, two blood samples (20 ml in total) will be taken. This corresponds to the standard of care. During the other visits blood samples will only be taken by discretion of the treating physician. If patients returned to their referring hospital or if visits are too stressfull, the T2 and T3 visits will be telephone calls. During these calls patients will answer questions about the presence of fever, jaundice and abdominal pain. 1 year after inclusion the treating physician will be contacted about late complications and vital status. Complications according to the Clavien-Dindo grading system (see Table 2.) and reinterventions are scored at each follow-up.

#### **Quality of life**

Patients complete questionnaires (QLQC30/BIL21) (see Appendix C and D) at the day of informed consent, and at 14 days, 28 days, and 90 days after the first intervention.

#### **Table 2. Classification of interventional complications**

Grade I	Any deviation from the normal postoperative course without the need for pharmacological treatment or surgical, endoscopic, and radiological interventions Allowed therapeutic regimens are: drugs as antiemetics, antipyretics, analgetics, diuretics, electrolytes, and physiotherapy. This grade also includes wound infections opened at the bedside
Grade II	Requiring pharmacological treatment with drugs other than such allowed for grade I complications
Grade III	Requiring surgical, endoscopic or radiological intervention
Grade IIIa	Intervention not under general anaesthesia
Grade IIIb	Intervention under general anaesthesia
Grade IV	Life-threatening complication (including CNS complications)* requiring IC/ICU management
Grade IVa	Single organ dysfunction (including dialysis)
Grade IVb	Multiorgan dysfunction
Grade V	Death of a patient

\*Brain hemorrhage, ischemic stroke, subarachnoidal bleeding, but excluding transient ischemic attacks. CNS, central nervous system; IC, intermediate care; ICU, intensive care unit.

#### 8.4 Withdrawal of individual subjects

Subjects can leave the study at any time for any reason if they wish to do so without any consequences. The investigator can decide to withdraw a subject from the study for urgent medical reasons.

##### 8.4.1 Specific criteria for withdrawal (if applicable)

Not applicable.

#### 8.5 Replacement of individual subjects after withdrawal

Not applicable, no replacement will take place.

#### 8.6 Follow-up of subjects withdrawn from treatment

If patients returned to their referring hospital or if visits are burdensome, the T2 and T3 visits will be telephone calls. During these calls patients will answer questions about the presence of fever, jaundice and abdominal pain.

#### 8.7 Premature termination of the study

The Sponsor may decide to terminate the study prematurely based on the following criteria:

- There is evidence of an unacceptable risk for study patients; The safety and feasibility will be monitored after 5 patients. The presence of sepsis,

---

cholangitis, bleeding, number of scheduled and unscheduled reinterventions and mortality rate within 90 days will be evaluated.

- There is reason to conclude that it will not be possible to collect the data necessary to reach the study objectives and it is therefore not ethical to continue enrolment of more patients; for example insufficient enrolment that cannot be improved.

The Sponsor will promptly notify all concerned investigators, the Ethics Committee(s) and the regulatory authorities of the decision to terminate the study. The Sponsor will provide information regarding the time lines of study termination and instructions regarding treatment and data collection of enrolled patients.

## 9. SAFETY REPORTING

### 9.1 Temporary halt for reasons of subject safety

In accordance to section 10, subsection 4, of the WMO, the sponsor will suspend the study if there is sufficient ground that continuation of the study will jeopardise subject health or safety. The sponsor will notify the accredited METC without undue delay of a temporary halt including the reason for such an action. The study will be suspended pending a further positive decision by the accredited METC. The investigator will take care that all subjects are kept informed.

### 9.2 AEs, SAEs and SUSARs

#### 9.2.1 Adverse events (AEs)

Adverse events are defined as any undesirable experience occurring to a subject during the study, whether or not considered related to the experimental intervention. Adverse events (grade 3 or higher) reported spontaneously by the subject or observed by the investigator or his staff will be recorded.

#### 9.2.2 Serious adverse events (SAEs)

A serious adverse event is any untoward medical occurrence or effect that

- results in death;
- is life threatening (at the time of the event);
- requires hospitalization or prolongation of existing inpatients' hospitalization;
- results in persistent or significant disability or incapacity;
- is a congenital anomaly or birth defect; or
- any other important medical event that did not result in any of the outcomes listed above due to medical or surgical intervention but could have been based upon appropriate judgement by the investigator.

An elective hospital admission will not be considered as a serious adverse event.

Progression of the disease under study is not considered an SAE unless it meets any of the seriousness criteria mentioned above.

The principal investigator will decide whether or not the SAE is related to study treatment. The decision will be recorded on the serious adverse event report. The assessment of causality is made by the local investigator using the following:

RELATIONSHIP	DESCRIPTION
UNRELATED	There is no evidence of any causal relationship
RELATED	There is evidence to suggest a causal relationship

The sponsor will report the SAEs through the web portal *ToetsingOnline* to the accredited METC that approved the protocol, within 7 days of first knowledge for SAEs that result in death or are life threatening followed by a period of maximum of 8 days to complete the initial preliminary report. All other SAEs will be reported within a period of maximum 15 days after the sponsor has first knowledge of the serious adverse events.

### 9.2.3 Suspected unexpected serious adverse reactions (SUSARs)

Not applicable.

### 9.3 Annual safety report

Not applicable.

### 9.4 Follow-up of adverse events

All AEs will be followed until they have abated, or until a stable situation has been reached. Depending on the event, follow up may require additional tests or medical procedures as indicated, and/or referral to the general physician or a medical specialist.

SAEs need to be reported till end of study within the Netherlands, as defined in the protocol.

### 9.5 Data Safety Monitoring Board (DSMB)

A Data and Safety Monitoring Board will not be installed. Monitoring of data and safety will be performed as described in the monitoring plan (see chapter 12.2: Monitoring and Quality Assurance).

## 10. STATISTICAL ANALYSIS

### 10.1 Primary study parameter(s)

Pilot cohort and overall analysis

The primary outcomes for safety are OS is defined as the interval between the day of intervention and date of death or last follow-up. This will be estimated using the Kaplan-Meier method.

### 10.2 Secondary study parameter(s)

Pilot cohort and overall analysis

The secondary outcomes for safety and feasibility are the stent-related complications, the amount of reinterventions in 90 days, absolute and relative (%) decrease of bilirubin in 14 days, infectious biliary complications (i.e. cholangitis and cholecystitis), technical success of stent placement at initial drainage procedure, proportion of patients that started with palliative chemotherapy and cost-effectiveness. The proportion and 95% confidence interval will be calculated for the continuous variables. The median and interquartile range will be measured for the numeric variables.

Expansion cohort

QoL is measured with (QLQC30/BIL21) (see Appendix C and D). Repeated measurement analysis will be used to evaluate within group differences. the repeated measurements will be analyzed separately using linear mixed models with correction for the baseline score (added as covariate). The single items in the QLQ-C30 will be analyzed using (ordinal) logistic regression with random effects. The BIL21 questionnaire will also be used as utility measure for the cost-effectiveness analysis.

We will perform a cost-effectiveness analysis to evaluate the impact of percutaneous placement of metal stents in patients with unresectable pCCA. The cost-effectiveness analysis from the healthcare sector perspective will consider direct medical costs of both strategies. Prospective patient-level cost data collection for each patient in the trial would be ideal but is too expensive to collect. Instead, we will model costs in a decision model using probabilities of events and unit costs of interventions.

Data from a comparable matched cohort of both participating centers of patients treated with endoscopic drainage in the period before the current trial, will be used as a comparison. The health effects will be expressed in quality-adjusted life years (QALYs). The QALY combines the number of life years with the quality of life measured with the EQ-5D utilities. The cost-effectiveness of percutaneous placement of metal stents will be expressed as the incremental costs per QALY gained to allow comparison with other (unrelated) health care

---

interventions. In addition, we will determine the degree of uncertainty regarding the cost-effectiveness of percutaneous placement of metal stents by performing probabilistic sensitivity analyses. We will present the uncertainty of cost-effectiveness estimates using scatter-plots on a cost-effectiveness plane, cost-effectiveness acceptability curves, and value of information analysis. The project leader ([name]) has a PhD in cost-effectiveness analysis.

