#### Second expansion cohort (30 patients)

Nine months (July 1st, 2022) after approval for the first expansion cohort of 27 patients, we have included 20 additional patients in Erasmus MC. For the first 30 patients (10+20), the outcomes are compared with our historical cohort for endoscopic biliary drainage in Table 1.

Table 1

	Number of patients	Reintervention within 90 days	Mortality within 90 days	Administration of systemic chemotherapy
Endoscopic drainage – retrospective cohort	90	75%	35%	20%
Primary percutaneous stenting - TESLA trial	30	6%	3%	75%

Because of these favorable results, we are currently designing a multicenter randomized controlled trial (RCT) to compare this intervention with the standard of care (i.e. endoscopic biliary drainage). Six additional centers will participate in this trial. To avoid any aspect of

---

learning curve regarding the intervention within the RCT, each participating center is required to perform the study intervention in 5 patients in this phase II study, before accruing patients in the RCT. Therefore, a second expansion cohort of 30 patients (i.e. 5 patients per center for 6 centers) is required.

A total of 67 patients (10+27+30) will be included and analyzed for the study endpoints. The expected inclusion period of the additional 30 patients, in six participating centers, is one year.

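### Section 10.2 attaches proportions to continuous variables, probably a slip, and leaves the reintervention count with a median and IQR that is likely to read 0 (0-0)

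*Protocol*

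**What the plan says.** Section 10.2 of the protocol lists the secondary safety and feasibility outcomes for the pilot cohort and the overall analysis. They include stent-related complications, "the amount of reinterventions in 90 days", bilirubin decrease, infectious biliary complications, and "technical success of stent placement at initial drainage procedure, proportion of patients that started with palliative chemotherapy and cost-effectiveness".

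Two rules for summarising them follow:

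- "The proportion and 95% confidence interval will be calculated for the continuous variables"
- "The median and interquartile range will be measured for the numeric variables"

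The paragraph has no rule for binary or categorical variables. Section 8.1.2 defines two of the outcomes in these terms:

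- "Number of scheduled and unscheduled reinterventions within 90 days"
- "Absolute and relative (%) bilirubin decrease after 14 days"

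Table 1, in the study design section under the second expansion cohort, reports reintervention within 90 days as a percentage: 6% of the first 30 trial patients against 75% of 90 patients in the retrospective endoscopic cohort.

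**The concern.** There are two separate problems.

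First, a proportion is not defined for a continuous variable unless the variable is dichotomised. Bilirubin decrease is both continuous and numeric, so it falls under both rules, and one of them cannot be carried out. Technical success, infectious complications and started chemotherapy are yes/no outcomes and fall under neither. The only confidence interval in the paragraph is attached to the wrong type of variable.

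Second, the reintervention endpoint is a count per patient. That makes it numeric, so its stated summary is a median and IQR. When most patients have no reintervention, the median and both quartiles are 0. The summary then carries no information about how many patients needed one and gives no precision.

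Fewer reinterventions is part of the stated hypothesis, and the reintervention rate is one of the three outcomes in Table 1 that the protocol cites when it announces the randomised trial. It is also reported there on a different scale from the one that section 10.2 implies. That leaves the choice of reported measure open after the results of 30 patients are known.

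**Working it through.** **Inputs.** The two rules are from section 10.2. The endpoint definition is from section 8.1.2. The 6% of 30 and 75% of 90 are from Table 1. The 67 patients to be analysed are from the study design section.

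**Step 1: the Table 1 figure.** 1/30 = 3.3%, 2/30 = 6.7%, 3/30 = 10%. Only 2/30 is close to 6%, so the printed figure is taken as 2/30 with the decimals cut off.

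**Step 2: which rule covers which endpoint, read literally.**

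| Endpoint | Type | Proportion rule (continuous) | Median and IQR rule (numeric) |
|---|---|---|---|
| Technical success | binary | no | no |
| Infectious biliary complications | binary | no | no |
| Chemotherapy started | binary | no | no |
| Stent-related complications | graded (Clavien-Dindo), ordinal | no | no |
| Bilirubin decrease | continuous | yes, but undefined | yes |
| Number of reinterventions | count | no | yes |

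If the word for continuous is replaced by categorical or binary, the first four rows gain a rule and bilirubin keeps only the median and IQR. The last row does not change.

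**Step 3: when the reintervention summary is 0 (0-0).** Let x be the number of patients with at least one reintervention, so that N − x patients have 0. With linear interpolation the upper quartile sits at ordered position 1 + 0.75 × (N − 1). For N = 67 this is 1 + 49.5 = 50.5, between the 50th and 51st values. It is 0 if at least 51 values are 0, that is, if x ≤ 67 − 51 = 16, and 16/67 = 23.9%. The corresponding limits are 2/10, 7/30 and 9/37. In the smaller groups the limit depends on the quartile definition: with position 0.75 × (N + 1) it is 1/10 and 6/30, while at N = 67 that position is 51 and the limit is again 16.

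**Step 4: probability of 0 (0-0) at N = 67.** This is P(X ≤ 16) with X binomial(67, true rate). One common rate for all 67 patients is an assumption.

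| True share with any reintervention | P(median 0, IQR 0-0) |
|---|---|
| 6% | >0.999 |
| 10% | >0.999 |
| 15% | 0.98 |
| 20% | 0.83 |
| 25% | 0.48 |
| 30% | 0.17 |

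At a true rate of 2/30, P(X ≥ 17) = 1.4 × 10⁻⁶. Put another way, with 2 events in the first 30 patients, at least 17 − 2 = 15 of the remaining 67 − 30 = 37 (41%) would need a reintervention before the upper quartile left 0. At the historical 75% the median would be at least 1, so the empty summary comes from the rule combined with this trial's low rate.

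**Step 5: what a proportion would show.** The exact (Clopper-Pearson) limits are the 0.025 quantile of Beta(x, n − x + 1) and the 0.975 quantile of Beta(x + 1, n − x).

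- 2/30 = 6.7%, 95% CI 0.8% to 22.1%
- If the rate held at N = 67 (assumption): 4/67 = 6.0%, 1.7% to 14.6%; or 5/67 = 7.5%, 2.5% to 16.6%

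Under the median and IQR rule, all three data sets give 0 (0-0).

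**The case against.** The strongest reply is that this is a one-word error. Two consecutive sentences, one giving a proportion with a CI and the other a median with an IQR, are the usual categorical/numeric pair. The chemotherapy endpoint is itself worded as a proportion, and Table 1 uses percentages throughout. A reader might infer from section 10.2 that the trial will report its binary endpoints without any confidence interval. The documents do not support that: a rule for proportions is present but mislabelled, and an analyst would very likely apply it to the binary outcomes. This part of the objection stands.

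A reader might also infer that the reintervention result is bound to be 0 (0-0). It is not. Section 10.2 does not say by name which rule applies to reinterventions; that follows from their definition as a number. The outcome also depends on the rate. The 6% comes from 30 patients at one centre, whereas the last 30 patients are to come from six centres contributing their first five cases each. The endpoint counts scheduled reinterventions, and Table 1 does not say whether its figure does. This stands too, and it is why the claim is given as a range over the true rate.

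Finally, these are secondary, descriptive outcomes with no test or decision rule attached, nothing prevents the sponsor from reporting a percentage as well, and a SAP may do so. That limits the weight of the point but does not remove it. The protocol sentence is wrong as it stands, and correcting the slip leaves reinterventions under the median and IQR rule.

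**Conclusion.** The point holds in two parts of unequal weight. The wording error is certain, but it is probably a slip that most analysts would read correctly. The reintervention summary is the more substantive part because it survives the correction. At 67 patients it is uninformative for any observed share up to 16/67, and it stays more likely than not to be so at a true rate of 20% (0.83), falling to about even at 25% (0.48).

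This rests on reading the endpoint as numeric, on taking Table 1's 6% as 2/30, and, for the probabilities, on one common rate across cohorts and centres. It does not affect the Kaplan-Meier analysis of overall survival or the calculation behind the 37 patients. Nor does it show that the decision to plan the randomised trial was unsound: that trial was already being designed, on three outcomes taken together.

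**What to change.** Replace the two sentences in section 10.2 with rules by endpoint:

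1. Binary and categorical outcomes: n/N with a 95% CI, naming the interval method. Stent-related complications are also tabulated by Clavien-Dindo grade.
2. Bilirubin decrease, absolute and relative: median and IQR.
3. Reinterventions: the proportion of patients with at least one within 90 days with a 95% CI, scheduled and unscheduled separately, alongside the number per patient.

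It would also help to state whether the Table 1 figure includes scheduled reinterventions, so that the final result can be compared with it. A CI for the median, a mean count, or a cumulative incidence with death as a competing event are optional extras.

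The cost is two or three sentences in the protocol or SAP. No new data, patients or change of design are needed.

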#### Expansion cohort (27 patients)

After the inclusion of the first 10 patients has been completed, an expansion cohort will be added in which UMC Utrecht, Amsterdam UMC and Oslo University Hospital as participating centers will be added, in order to perform a multicenter phase-II trial. Following the analyses of the first 10 patients, another 27 patients will be included to assess the effectiveness and safety of direct SEMS placement for palliative treatment of a primary malignant perihilar stricture. In total 37 patients will be included and analyzed for the study endpoints. The expected inclusion period of the additional 27 patients is two years.

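### The QoL model enters the baseline score as a covariate although the aim is within-group change in one arm, so change from before to after drainage is not a model parameter

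*Protocol*

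**What the plan says.** Section 10.2 (Expansion cohort) gives the aim of the QoL analysis: "Repeated measurement analysis will be used to evaluate within group differences". It then names the method, "linear mixed models with correction for the baseline score (added as covariate"), and gives the single items of the QLQ-C30 an ordinal logistic model with random effects.

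Section 8.3 (Quality of life) sets the measurement times: "at the day of informed consent, and at 14 days, 28 days, and 90 days after the first intervention". The consent-day form is therefore the only measurement before drainage.

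There is one arm. Section 8.2, headed "Randomisation, blinding and treatment allocation", is answered as not applicable. The only comparator in Section 10.2 is "Data from a comparable matched cohort of both participating centers of patients treated with endoscopic drainage in the period before the current trial", and it serves the cost-effectiveness comparison, not the QoL model.

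The protocol does not say whether the modelled outcome is the score or the change, whether baseline is centred, or whether the baseline record also stays among the outcomes.

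**The concern.** A baseline covariate is most useful when arms are compared, where it adds precision and corrects chance imbalance. This model has no second arm. Moving the only pre-drainage score to the predictor side removes the reference point from which a before-after change would be estimated.

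The protocol's Summary and Introduction name the patient's wellbeing as one purpose of drainage, and a baseline form is collected. A reader will therefore expect the QoL result to show whether scores change after stenting. Under the stated model, that result is either not produced or has to be assembled outside the model, and the most obvious way of assembling it gives intervals that are too narrow. In addition, a patient without a baseline form drops out of a covariate model unless the baseline is imputed, even if follow-up forms exist.

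**Working it through.** **Inputs from the protocol.** One arm (Section 8.2). Four QoL time points: consent day and days 14, 28 and 90 (Section 8.3). Cohort sizes from Section 3: "another 27 patients will be included to assess the effectiveness and safety" and "a second expansion cohort of 30 patients (i.e. 5 patients per center for 6 centers) is required". Section 2 assigns QoL to the expansion cohort in the singular, so n = 27 is one reading. If both expansion cohorts complete QoL, n = 27 + 30 = 57.

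**Assumptions, not in the protocol.** The correlation rho between baseline and follow-up scores, taken from 0.3 to 0.9; the same SD s at each visit; for the simulation, SD 20 and a true change of 10. The protocol states no QoL sample size, SD, correlation or precision, so there is no planned figure to reproduce.

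**Step 1: what the stated model estimates.** With outcomes at days 14, 28 and 90 and baseline as covariate, the visit coefficients are mean scores at a given baseline value, or differences between follow-up visits. None of them is follow-up minus baseline.

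**Step 2: deriving the change anyway.** Evaluate the adjusted mean at the average baseline and subtract that average. With complete data this equals the mean follow-up score minus the mean baseline score, so the estimate is unbiased. Its error is not correctly stated:

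- Model-based variance, with the baseline mean treated as fixed: s²(1 − rho²)/n
- Actual variance of the mean change: 2s²(1 − rho)/n
- Ratio of variances: (1 − rho)(1 + rho) / [2(1 − rho)] = (1 + rho)/2
- Ratio of standard errors: sqrt((1 + rho)/2), which does not depend on n

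The actual rejection rate of a nominal two-sided 5% test is 2 × [1 − Φ(1.96 × ratio)]:

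| rho | SE ratio | 1.96 × ratio | Rejection under no change | Coverage of nominal 95% CI |
|---|---|---|---|---|
| 0.3 | 0.81 | 1.58 | 11.4% | 88.6% |
| 0.5 | 0.87 | 1.70 | 9.0% | 91.0% |
| 0.7 | 0.92 | 1.81 | 7.1% | 92.9% |
| 0.9 | 0.97 | 1.91 | 5.6% | 94.4% |

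A simulation of 20,000 trials per setting with 57 patients and no true change gave 11.35%, 9.05% and 7.02% at rho 0.3, 0.5 and 0.7, against 5.0% for the contrast with baseline kept as an outcome.

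**Step 3: check with fitted mixed models.** Random-intercept REML models, 4,000 trials per setting, day 90 minus baseline, complete data:

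| n, rho | Approach | Model SE | Empirical SE | Coverage |
|---|---|---|---|---|
| 57, 0.5 | change derived with baseline as covariate | 2.29 | 2.63 | 90.7% |
| 57, 0.5 | baseline as repeated outcome | 2.65 | 2.63 | 94.9% |
| 27, 0.3 | change derived with baseline as covariate | 3.65 | 4.65 | 87.4% |
| 27, 0.3 | baseline as repeated outcome | 4.53 | 4.65 | 94.3% |

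The formula agrees. For n = 57 and rho = 0.5 it gives 20 × sqrt(0.75/57) = 2.29 for the model and 20 × sqrt(1/57) = 2.65 for the truth.

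**Step 4: baseline as both outcome and covariate.** With n = 57, rho = 0.5 and complete data, the SE is about right (2.65 against 2.63, coverage 94.9%). With about 37% outcome-dependent dropout at day 90 (assumed), the estimate is 10.39 against a true 10, the SE 3.06 against 3.20, and coverage 93.6%. The covariate adds nothing here and does slight harm under dropout.

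**The case against.** The strongest reply is that the protocol fixes only the covariate. The outcome vector, the covariance structure and the contrasts are normal SAP content, and the SAP is not shown. This stands for those details, and their absence is not the point made here. It does not remove the mismatch, because the protocol names the covariate and the within-group aim together. An SAP that follows it inherits the problem, and one that drops the covariate departs from the protocol.

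Second, differences among days 14, 28 and 90 are also within-group differences, and the stated model estimates them validly. This stands. The protocol nowhere writes that the QoL question is change from baseline; that is inferred from the collected baseline form and from the stated purpose of drainage. Nor is a baseline covariate wrong in itself in one arm, since it can describe follow-up scores given the starting score.

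Third, a reader might infer that the stated model must give too many false improvements, at 7% to 11%. The documents do not support that. The rates apply only if the change is derived as in Step 2, and Section 10.2 states neither that step nor a significance test for QoL. Keeping baseline as both outcome and covariate gives about correct standard errors with complete data (Step 4), so counting it twice is not a material fault in itself.

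Last, rho is unknown, and at 0.9 the effect is negligible. This too stands.

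**Conclusion.** The point holds as a mismatch between a stated aim and a stated method. In its usual meaning the model does not estimate change from before to after drainage, although the trial has one arm and collects a baseline form. Comparisons among follow-up visits are sound.

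The numerical harm is conditional. If the change is derived as the adjusted mean minus the average baseline, standard errors are about 19%, 13%, 8% or 3% too small at rho 0.3, 0.5, 0.7 or 0.9. The sample size hardly matters. The figures rest on an assumed rho and equal SDs across visits. The primary endpoint, overall survival, is untouched, so this should be corrected but does not threaten the main result.

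**What to change.** Reword the QoL model in Section 10.2 as follows:

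- Use the scores at all four time points (consent day, days 14, 28 and 90) as outcomes in the linear mixed model.
- Enter time as a categorical fixed effect and specify a within-patient covariance, for example unstructured.
- Drop the baseline score as a covariate.
- Report day 14, day 28 and day 90 minus baseline, each with a 95% CI.

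The covariate wording is attached to the linear models, not to the ordinal ones. Where change from baseline is also reported for single items, use the same time contrasts there, so that all QoL results answer one question.

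The cost is a change of wording. The data, the visits and the software stay the same, and patients with a missing baseline form but later forms remain in the analysis.
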